**Table I: Parameter ranges for TMS protocols proposed intensities of stimulator output**

Protocol	Intensity (% Active MT)	Frequency	Pulses/trial or train	Inter-train-interval (sec)
Single pulse TMS	$\leq 120$	$\leq 1$ Hz	1	1
Paired pulse TMS	$\leq 100$	$\leq 0.2$ Hz	2	5
Triple pulse TMS	$\leq 80$	3 x 40-60 Hz at 0.2 Hz	3	5

**Figure 1: Relationship of single-pulse and repeated pulse protocols (Single and paired pulse protocols) to rTMS consensus safety guidelines from Table 4 of Rossi et al. (2009). Blue box indicate where on the table single and paired TMS pulse protocol parameters comply.**

## EMG & Motor Thresholding

Electromyography (EMG) is used to accurately and precisely measure electrical potentials in the muscles. Recording electrodes are taped/stuck (if they have a sticker backing) to the skin above a muscle of interest following a brief cleaning of the area using an alcohol wipe. An amplifier is used to amplify small, recorded muscle potential signals. This set up can be used to measure the latency and amplitude ( $\mu\text{V}$ ) of Motor Evoked Potentials (MEPs) in the muscles produced by TMS over the contralateral motor cortex.

The quantified amplitudes of MEPs evoked by TMS are conventionally used to determine motor thresholds for calibration of stimulator output strength across different types of TMS protocols. In this study, the proposed TMS protocols will utilize stimulator output strengths measured as a function of active motor thresholds, as indicated in Table I.

To determine an individual participant's active motor threshold (AMT), we will apply single pulses of TMS to primary motor cortex. AMT is defined as the minimum stimulator intensity needed to elicit a  $100\ \mu\text{V}$  or greater EMG response in a target muscle in 50% of pulses (e.g., 5/10) applied to the contralateral primary motor cortex when the target muscle is voluntarily contracted using 10% of maximum voluntary force.

AMT will be determined by initializing the stimulator's output to a proportion of its maximum output that is expected to yield a 50% probability of eliciting an EMG of the criterion intensity ( $50\ \mu\text{V}$  for resting MT, or  $100\ \mu\text{V}$  for active MT). The intensity of stimulation will then be adjusted incrementally to as much as 100% of stimulator output until the AMT is achieved. The TMS pulses used in this procedure will be delivered no faster than 1 pulse every 5 sec (.2 Hz). This slow rate is well within established safety limits (see Figure 1).

If our highest motor threshold (120% active motor threshold) corresponded to 100% stimulator output, the participant's active motor threshold would be  $\sim 83$ . This is highly unlikely in TMS studies without EEG. However, in studies in which the coil is placed further from the scalp due to large active electrodes, motor thresholds increase due to a quick dropoff in magnetic field strength with distance. Therefore, we will cap the maximum motor threshold at 76. If a participant does not have a motor threshold  $\leq 76$ , they will be paid for a full TMS-EEG session, but then excluded from the study and allowed to leave after the motor thresholding procedure.

**THE BLUE TEXT IN THE FOLLOWING SECTIONS IS A GUIDE TO ENSURE ALL RELEVANT INFORMATION IS INCLUDED IN YOUR APPLICATION. YOU MAY DELETE THE BLUE TEXT BEFORE SUBMISSION**

**4. Participant Population.** *In order to approve research, the IRB must determine that the selection of participants is equitable and reasonably related to the purpose and aims of the research. The IRB must also consider whether adequate safeguards are in place to minimize any risks that are unique to vulnerable populations. To make this determination, the IRB must review all methods and materials used to contact and recruit potential participants, including letters, flyers, emails, etc.*

[figure not shown]
It is necessary to test human participants in this multi-modal study. We will link our EEG and perceptual outcomes to cellular and circuit mechanisms with our unique biophysically principled model of human somatosensory cortex (SI). Additionally, due to the complexity and highly folded nature of the human brain, TMS effects may not directly translate to other species; indeed, one goal of this proposed work is to understand the effects of TMS localized specifically to human SI in order to inform development of therapeutic TMS protocols for clinical human use. Finally, due to the relative size of the human brain in comparison with the TMS coil, TMS is capable of having a more localized and thus interpretable impact on somatosensory processing than if we were to use a smaller animal model.

This project encompasses two separate studies; one in which EEG data is collected concurrent with TMS, and one in which no stimulation is given. Both studies incorporate the tactile detection task previously described, and require an MRI. We would like to recruit 25 participants for each of the two studies, and participants may take part in only one or both studies if they meet the inclusion criteria described. An MRI is needed only once, and the same MRI can be used for both studies. For this reason, the individual visits required for each of the two studies are hereafter all described as "sessions" in order to be less confusing for the participant. Selection of participants for either of the two studies will simply depend on which experiments we are ready to begin/ focus on analyzing when participants express interest. After

v. 01/21/2019

participants take part in an EEG session (with or without TMS), we will let them know that they may be able to participate in additional sessions, and ask if they are interested in returning for the other study.

We plan to recruit 25 healthy adults for experimental sessions consisting of EEG with TMS (sessions I, III and IV), and 25 individuals without TMS (sessions I & II). All recruited participants (including EEG with and without TMS) will take part in an MRI session once (session I) because the MRI data is required for analysis of EEG data, and for acquisition of TMS data. See illustration below.

Upon initial screening, we will let participants know whether they will take part in an EEG session with or without TMS, and that they may subsequently be invited to come back for up to two additional EEG sessions with or without TMS. Our goal is to acquire 25 datasets each of EEG data with and without TMS, respectively.

We plan to recruit healthy adult human participants (18-65 years old) to take part in this study from the Brown University community and greater Providence, RI, area. Participants of any gender, race, ethnicity, religion, sexual preference, residence or family composition will be included. All efforts will be made to include minorities and women in the studies, at the appropriate proportions for the local area. Recruitment will be initiated in response to an e-mail contact from the participant regarding an advertisement. Advertisements may be posted as flyers (see attached), or circulated electronically in e-mail digests and online. We will not initiate contact with students, but will wait for them to approach us for information about the studies.

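### The motor-threshold search may rise to 100% of stimulator output although exclusion is already settled at 76, and no sentence links the two limits

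*Protocol*

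**What the plan says.** All the relevant text is in the protocol, section 3, under EMG & Motor Thresholding.

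- **Definition.** "AMT is defined as the minimum stimulator intensity needed to elicit a" response of 100 µV or more in 50% of pulses, with 5 out of 10 given as an example.
- **Start of the search.** It begins by "initializing the stimulator's output to a proportion of its maximum output that is expected to yield a 50% probability" of a criterion response. No number is given.
- **Progress and end of the search.** Intensity is then "adjusted incrementally to as much as 100% of stimulator output until the AMT is achieved". Pulses are "delivered no faster than 1 pulse every 5 sec (.2 Hz").
- **Eligibility.** The section works out the threshold at which 120% of AMT would need full output (about 83) and notes that thresholds rise when large electrodes move the coil away from the scalp. It concludes: "Therefore, we will cap the maximum motor threshold at 76". Someone without a threshold at or below 76 is paid for a full session, "but then excluded from the study and allowed to leave after the motor thresholding procedure".

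Neither limit refers to the other. The search text has two end points: reaching the AMT, or reaching 100% of output. The eligibility text has one cut-off, 76.

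**The concern.** The AMT is the lowest intensity that meets the criterion. If the criterion is not met at 76, the threshold cannot be at or below 76 under the protocol's own definition, and the exclusion decision is made. A result on the borderline might justify repeating the test at the cap, but not pulses above it. Followed literally, the search text still lets staff go on raising output, and the participant leaves only once thresholding is over.

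What is at stake is participant burden and clear instructions for staff. Pulses given after the decision is settled change no eligibility outcome and give no data to the TMS study. In section 7, the protocol itself names high stimulator output among the factors that increase seizure risk, and it says that high-output repetitive stimulation can feel sharp or painful. It also recalls that the ethics board must find risks minimised. Exposure with no decision attached to it is hard to justify under that standard, even when the exposure is small. The protocol treats a threshold above the cap as a case it expects to meet, since it gives a reason for the cap and writes a payment rule for those who exceed it.

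**Working it through.** **Reproducing the plan's own figure.** The section says "If our highest motor threshold (120% active motor threshold) corresponded to 100% stimulator output, the participant's active motor threshold would be" about 83. Check: 100 / 1.20 = 83.3, which agrees. This also supports reading 76 as a percentage of stimulator output, because it is set directly against that figure. The document prints no unit, so this is an inference.

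**Gap between the two limits.** 100 − 76 = 24 points of output.

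**Comparison with an eligible participant.** Table I allows single pulses up to 120% of AMT. At the cap this is 76 × 1.20 = 91.2% of output. The search ceiling of 100% is therefore 8.8 points above the most that a participant exactly at the cap could receive in the single-pulse protocol.

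**Extra pulses.** The protocol fixes neither the step size nor the number of pulses per level. Assumptions: 10 pulses per level (from the 5-out-of-10 example), an ascending search, equal steps above 76, and the fastest permitted rate of one pulse per 5 s.

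Pulses = levels tested above 76 × 10. Minimum time in minutes = pulses × 5 / 60.

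| Where the search ends | Step (points) | Levels above 76 | Pulses | Minimum time |
|---|---|---|---|---|
| First level above the cap | 1 to 5 | 1 | 10 | 0.8 min |
| AMT of 80 | 1 | 4 | 40 | 3.3 min |
| AMT of 80 | 5 | 1 (at 81) | 10 | 0.8 min |
| Top of range | 5 | 4 (81, 86, 91, 96) | 40 | 3.3 min |
| Top of range | 2 | 12 | 120 | 10 min |
| Top of range | 1 | 24 | 240 | 20 min |

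With 5-point steps, a short last step from 96 to 100 would add one level, giving 50 pulses. The search stops when the AMT is reached, so the top-of-range rows apply only to someone whose threshold is near or above 100% of output.

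**What cannot be computed.** The documents give no distribution of motor thresholds with the EEG cap in place. The expected number of people above 76 among the 25 planned for the TMS study is therefore unknown.

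**The case against.** The strongest reply is that nothing here is a strict contradiction. One sentence gives the outer range of a measurement and the next gives a cut-off on its result, and a range may be wider than a cut-off. The search text permits output up to 100% and does not compel it. The exclusion is worded as not having a threshold at or below 76, so staff need not find the true value, and the two statements can be read together as allowing the search to end at the cap. This stands in part. A reader might infer that the protocol requires stimulation up to 100%, and it does not. But the search text names only two end points, neither of them the cap, so the sensible reading is left to each operator.

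The second reply concerns risk. A reader might infer a serious safety hazard from the words 100% of output. The documents do not support that. The pulses are single and no faster than 0.2 Hz, a rate the protocol places within established limits. An ascending search that stops at the AMT stays close to the person's own threshold, whereas Table I allows up to 120% of it for single pulses. The protocol also attributes high thresholds here to the coil's distance from the scalp, so high machine output does not mean correspondingly high exposure of the cortex. This reply stands.

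A third reply is that pulses above 76 might have a use, for example when a search starts high and comes down. The starting level is not given as a number, so this is possible. The protocol describes no such use, however, and it would not explain continuing upward after the criterion has failed at 76.

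**Conclusion.** The point holds as an inconsistency between the end point of the search and the exclusion rule. As written, a participant may receive pulses over as much as 24 points of output after exclusion is settled. The extra exposure ranges from about 10 pulses (under a minute) to an upper bound of about 240 pulses (20 minutes). It would be wrong to apply the upper bound to every excluded participant: it needs 1-point steps and a climb all the way to 100%.

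The size rests on three assumptions: that 76 is a percentage of stimulator output, that 10 pulses are given per level, and that steps are 1 to 5 points. The conclusion itself rests only on the first of these and on AMT being a minimum. How many people are affected is unknown and absolute risk is low. A reader might also infer an effect on the results. There is none, because under the present cap these participants are excluded in either case, so the analysis and the planned number of datasets are untouched. It is a modest point, worth correcting because the remedy is nearly free.

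**What to change.** Reconcile the two statements in EMG & Motor Thresholding so that the end point of the search and the exclusion rule agree. Alternatively, if pulses above the cap serve a purpose, state that purpose and its limits. Printing the unit of the 76 in the same edit would remove the need for inference. This review does not propose a level for either limit, which is for the investigators and the ethics board to decide.

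The cost is a one-sentence amendment. If only the wording on the end of the search changes, nobody's eligibility changes and no usable data are lost. If the cap itself were changed, eligibility would change with it and the new value would need its own justification.

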#### Inclusion criteria

- 1) Ability to provide informed consent/ assent
- 2) Age: 18-65 years
- 3) English fluency: participants must be able to understand screening questionnaires and task instructions spoken/ written in English.
- 4) Right handed: to reduce heterogeneity related to hand dominance, since our task involves touch perception on the hand, and examination of neural correlates in lateralized brain regions.

#### Exclusion criteria

Participants will be screened to exclude individuals with co-occurring neurological or medical conditions that might confound the results. We will also exclude subjects for which TMS or MRI might result in increased risk of side effects or complications:

- 1) History of fainting spells of unknown or undetermined etiology that might constitute seizures
- 2) History of seizures, diagnosis of epilepsy, or immediate (1st degree relative) family history epilepsy
- 3) Any progressive (e.g., neurodegenerative) neurological disorder
- 4) Chronic medical conditions that may cause a medical emergency in case of a provoked seizure (cardiac malformation, cardiac dysrhythmia, asthma, etc.)
- 5) Metal implants (excluding dental fillings)
- 6) Pacemaker
- 7) Implanted medication pump or cochlear implant

v. 01/21/2019

- 8) Vagal nerve stimulator
- 9) Deep brain stimulator
- 10) TENS unit (unless removed completely for the study)
- 11) Ventriculo-peritoneal shunt
- 12) Signs of increased intracranial pressure
- 13) Intracranial lesion
- 14) History of head injury resulting in prolonged loss of consciousness
- 15) Pregnancy
- 16) Participants who have received prior TMS for medical treatment purposes.
- 17) Intellectual Disability or autism spectrum disorder (ASD)
- 18) Active psychosis, diagnosis of unipolar depression or bipolar disorder, active severe substance use disorders (within the last month), or active suicidal intent or ideations.
- 19) Conditions that may result in the inability to effectively carry out the tactile detection task, including loss of feeling, neuropathy or nerve damage in the hands or feet, chronic pain or fibromyalgia, and pain due to cancer, infection or arthritis.
- 20) If the participant is actively taking any of the medications that increase risk from TMS as indicated below, or if they have ingested any alcohol or any other drugs of abuse (see <https://www.drugabuse.gov/drugs-abuse>) on the day of the study session (prior to the session), they will be subject to exclusion from this study.

During the recruitment/screening process, participants will be asked to refrain from alcohol or any other drugs of abuse (see <https://www.drugabuse.gov/drugs-abuse>) on the day of the study session (prior to the study session). They will be told that a reasonable/normal amount of caffeine and/or nicotine is allowed on the day of the study session, however they will be asked to refrain from these substances 3 hours prior to any EEG (with or without TMS) study session. Participants will be encouraged to try to follow their normal routine as closely as possible on the day of the study session.

Please refer to the '[name] Initial Contact and Screening Form', the '[name] Participant Information and Secondary Screening Form', and the 'Brown University MRF Magnetic Resonance (MR) Procedure Screening Form for Research Subjects'.

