### List of contraindicated drugs

As documented in Rossi et al. (2009), taking one the following drugs may lower seizure thresholds. Note, however, that this is not an exhaustive list. Moreover, it is a list that may be out of date. Thus, any medication being taken by a participant will be cross-referenced against an updated list maintained on <https://www.epilepsy.com/learn/professionals/resource-library/tables/drugs-may-lower-seizure-threshold> AND reviewed by a TMS trained physician [REDACTED] to determine its potential to alter risk for seizure with TMS.

This list of drugs is current as of the time of the writing of the protocol. It is only stated that it may be out of date because new drugs are constantly developed and for that reason we will rely primarily on the judgement of the medical doctor and not on this list.

Imipramine  
 Amitriptyline  
 Doxepine  
 Nortriptyline  
 Maprotiline  
 Chlorpromazine  
 Clozapine  
 Foscarnet  
 Ganciclovir  
 Ritonavir  
 Amphetamines  
 Cocaine  
 MDMA (ecstasy)  
 phencyclidine (PCP, angel's dust)  
 ketamine  
 gamma-hydroxybutyrate (GHB)

v. 01/21/2019

alcohol  
theophylline  
mianserin  
fluoxetine  
fluvoxamine  
paroxetine  
sertraline  
citalopram  
reboxetine  
venlafaxine  
duloxetine  
bupropion  
mirtazapine  
fluphenazine  
pimozide  
haloperidol  
olanzapine  
quetiapine  
aripiprazole  
ziprasidone  
risperidone  
chloroquine  
mefloquine  
imipenem  
penicillin  
ampicillin  
cephalosporins  
metronidazole  
isoniazid  
levofloxacin  
cyclosporine  
chlorambucil  
vincristine  
methotrexate  
cytosine arabinoside  
BCNU  
Lithium  
Anticholinergics  
Antihistamines  
Sympathomimetic

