(3) Induced seizure: Though exceedingly rare even in patients with epilepsy, induction of a "generalized" seizure is the most severe adverse event associated with TMS. A seizure is an episode of excessive brain activity and stiff muscle activity (often referred to as a "convulsion" or "fit"). Seizure risk increases at high stimulator output intensities, at high frequencies of stimulation, with multiple repeated trains of stimulation, with long durations of stimulation, with short inter-train-intervals, and when stimulating participants with reduced seizure thresholds. However, the risk of seizure induction is minimal to negligible if TMS parameters are kept within the prescribed consensus safety parameters (Rossi et al., 2009), and participants are carefully screened for seizure risk. All the TMS protocols proposed here are will be within prescribed safety limits, and a health screening form will include questions to identify participants with potential seizure risk.

(4) TMS application site (scalp) discomfort/headache. The stimulation itself is felt as a tapping sensation on the scalp. The tapping induced by rTMS at high stimulator output intensity can feel sharper and even painful. In addition to a tapping or percussion sensation on the head, muscles and peripheral nerves in the head and face react to TMS with sensations such as twitching of superficial muscle groups.

As described above, acute, severe adverse events during the course of the TMS experiment could include things like superficial burns of participant's skin from TMS coil heating or induction of a generalized "seizure". Other adverse events such as fainting, severe headache, nonspecific stress reaction are possible with TMS and also with other types of brain research. Though our protocol and procedures minimize the risk of these adverse events occurring, all research personnel will be trained to observe the signs of an adverse event, terminate study procedures, and call Brown's Emergency Response System, if it appears a participant is experiencing an adverse event.

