## [name] TMS - Initial Contact & Screening Form

Name: \_\_\_\_\_

Date: \_\_\_\_\_

Email: \_\_\_\_\_

Birthdate: \_\_\_\_\_

Permission to call? If yes, best time: \_\_\_\_\_

Phone: \_\_\_\_\_

	Please check:	Yes	No
Do we have permission to leave a message on the phone?			
Are you right-handed?			
Are you a fluent English speaker?			
Have you ever had TMS or TCS before?			
Have you ever had an adverse reaction to TMS or TCS?			
Have you ever had a seizure?			
Do you have any family history of epilepsy?			
Have you ever had an unexplained loss of consciousness (i.e. fainting)?			
Do you suffer from chronic or severe headaches?			
Do you have any other cardiac, pulmonary or vascular medical issues?			
Have you ever had a stroke?			
Do you have any brain-related neurological or psychiatric illness?			
Have you been diagnosed with an intellectual/developmental disability or autism spectrum disorder (ASD)?			
Have you ever experienced any hallucinations or delusional behavior?			
Have you ever been diagnosed with any type of substance dependence?			
Have you ever had any serious head/brain injury or concussion?			
Have you ever had any surgery to your head/brain?			
Have you ever had any illness/infection that may cause brain damage?			
Do you have any metal objects/particles in your body (including your eyes)? E.g. metal prostheses, implants, surgical clips, shrapnel, grinding metal			
Do you have any implanted medical devices? E.g. pacemaker, cochlear implant			
Are you taking any medications (including OTCs)?			
Are you pregnant or potentially pregnant?			
Have you experienced any loss of feeling, neuropathy or nerve damage from diabetes, injury or any other cause?			
Do you have chronic pain or fibromyalgia?			
Do you have any pain due to cancer, infection or arthritis?			

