**Have you had any alcohol, nicotine, caffeine or other stimulants today?**

**If so, please indicate how much you had and at what time:**

---

---

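### The same-day substance question in the supplied screening forms is narrower than exclusion 20: it does not ask about non-stimulant drugs of abuse

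*Protocol*

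**What the plan says.** Section 4 of the protocol, Exclusion criteria, item 20, has two limbs. The first covers anyone "actively taking any of the medications that increase risk from TMS as indicated below". The second applies "if they have ingested any alcohol or any other drugs of abuse" on the day of a session, before it begins. In either case the consequence is that "they will be subject to exclusion from this study".

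The List of contraindicated drugs gives agents that may lower seizure threshold. Most are prescription drugs, but the list also contains alcohol, amphetamines, cocaine, MDMA, PCP, ketamine and GHB.

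Section 7, under TMS, item (3) on induced seizure, calls seizure risk minimal to negligible on two conditions: stimulation stays within consensus limits, and participants are carefully screened. On the second it says that "a health screening form will include questions to identify participants with potential seizure risk".

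The supplied form text has these drug-related items:

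- The Initial Contact & Screening Form asks "Are you taking any medications (including OTCs", and whether the person has ever been diagnosed with substance dependence.
- A further item asks for a list of current medications.
- The last item asks "Have you had any alcohol, nicotine, caffeine or other stimulants today", with amount and time.

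The text after the exclusion criteria says that participants will be asked to abstain from alcohol and drugs of abuse on the session day. Section 5, Recruitment Methods, adds a second questionnaire on each EEG or TMS-EEG day, meant to re-check for TMS exclusions.

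**The concern.** The rule covers every drug of abuse taken that day, but the visible question meant to apply it stops at stimulants. PCP, ketamine and GHB would not ordinarily be called stimulants, and the protocol itself lists them for their possible effect on seizure threshold. Other non-stimulant drugs of abuse fall in the same gap.

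Two things are at stake. The first is safety: the protocol rests part of its low-seizure-risk argument on what the screening form asks. The second is the data. A drug taken on one session day could alter tactile detection and EEG on that day only. Within a session, stimulation and no-stimulation trials share the same day. The comparison of the somatosensory site with the control site uses sessions at least one week apart (section 3, Experimental controls), so a one-day effect would not cancel there.

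**Working it through.** The plan states no figure on this point, so the check is a comparison of the rule with the questions.

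**Inputs.** The rule is item 20 with the List of contraindicated drugs. The questions are all the drug-related items in the supplied form text.

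| Drug use | Why it is relevant | Supplied question that would prompt disclosure |
|---|---|---|
| Alcohol, session day | Item 20, second limb; on the list | Yes, named |
| Amphetamines, cocaine, MDMA, session day | Item 20, second limb; on the list | Yes, if the participant counts them as stimulants |
| PCP, ketamine, GHB, session day | Item 20, second limb; on the list | None |
| Any other non-stimulant drug of abuse, session day | Item 20, second limb | None |
| Prescribed or over-the-counter drugs, current | Item 20, first limb, if on the list | Yes, medication items |
| Non-prescribed use of a listed drug, current but not that day | Item 20, first limb, only if its word for medications includes the listed recreational drugs | None that asks directly |

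The dependence question would flag users who have that diagnosis in any row. It asks about a diagnosis, not intake, so it says nothing about an undiagnosed or occasional user.

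**Count.** Seven listed substances have recreational use (my classification): alcohol, amphetamines, cocaine, MDMA, PCP, ketamine, GHB. The same-day question names 1 (alcohol) and can be read to cover 3 (amphetamines, cocaine, MDMA). That leaves 7 − 1 − 3 = 3 (PCP, ketamine, GHB).

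**Which form the same-day question belongs to.** It follows the Initial Contact form in the supplied text, but its reference to today suits a session-day form. If it is a session-day item, it is the check on item 20 and has the gap above. If it belongs to first contact, it concerns a different day, and no session-day question is visible at all. Neither reading closes the gap in the supplied text.

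**Other safeguards.** The abstinence request is an instruction, not a check. Alcohol is covered by the same request, yet the form also asks about it, so for alcohol the plan both instructs and asks. The physician review in the List of contraindicated drugs starts from medications that a participant is taking, so an undisclosed recreational drug would not reach it.

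**The case against.** The strongest objection is that the forms may not all be visible. The protocol names a Participant Information and Secondary Screening Form, and section 5 says that it re-checks TMS exclusions, notes changed medications and conditions, collects demographic information, and is reviewed before the session. No text under that title can be identified. The last questions shown may be a fragment of it, but they contain no demographic items, so the form is probably not complete here. This stands: the finding concerns the supplied questions, and the full form could already contain what is missing.

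It is also fair to say that participants are told to abstain, that a knowledgeable researcher conducts a pre-screening interview, and that doubtful cases go to a psychiatrist. These lower the chance of a problem, but none is a stated question about non-stimulant drugs of abuse.

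A reader might infer that users of these drugs pass screening into TMS, or that the forms cannot apply item 20. The documents do not support either. Item 20 makes people subject to exclusion rather than barring them outright, the dependence question would catch some users, and the session-day form cannot be judged. A reader might also want a probability that at least one participant is affected. The documents give no rate of use, so any such percentage would only restate an assumed rate.

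Finally, item 20 limits its drugs-of-abuse wording to the session day. Extending the point to earlier recreational use depends on how the first limb is read. That part is an interpretation, though a reasonable one given that recreational drugs are on the list.

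**Conclusion.** The mismatch is real and limited. No supplied question would reveal same-day use of a non-stimulant drug of abuse by someone without a dependence diagnosis, although item 20 makes such use a ground for exclusion. Three of the seven listed substances with recreational use are affected, along with unlisted non-stimulant drugs of abuse. How many participants this concerns, and how far it would disturb the comparison of the two stimulation sites, cannot be sized from the documents.

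The conclusion assumes that the supplied form text is what participants see, and that amphetamines, cocaine and MDMA would be reported as stimulants. If the full Secondary Screening Form already asks about drugs of abuse, the point falls away. Otherwise it is worth correcting, because the protocol relies on these questions in its seizure-risk argument and the change is small.

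**What to change.** 1. Check the full Secondary Screening Form. If it already asks about any drug of abuse on the session day, no change is needed to the same-day question.
2. If it does not, replace the closing category of the same-day question with wording that covers other stimulants or any other drugs of abuse, so that question and rule have the same scope. Keep the follow-up on amount and time, and make sure the question is put on the session day.
3. Because the contraindicated list contains recreational drugs, have the current-medication items state that they include the listed drugs when taken without a prescription.
4. Send any yes to the physician review already described in the List of contraindicated drugs.

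Item 20 and the list are left as they are; only the questions are brought into line. The cost is a few words on the forms, a minor IRB amendment, and a slightly more sensitive question. The answers remain self-report, so the change prompts disclosure but does not verify it.
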